## **OVERDOSE RESPONSE WITH NALOXONE INSTRUCTIONS:**

- **Primary Staff Person:**
  - Verify that the participant cannot be woken up by yelling their name loudly.
  - Then do a sternum rub on the participant’s chest using your knuckles.
  - Loudly announce to the participant, “**I am going to call 911 to get you medical help.**”
- **Primary Staff Person:** Ask a nearby staff person to be in the “Secondary Staff” role.
  - Tell them to “Call 911” and report, “a person is unconscious/not breathing” and give the location at [name], 2nd floor.
- **Secondary Staff Person:**
  - “Call 911” and report, “a person is unconscious/not breathing” and give the location at [name], 2nd floor.
  - Give First Responders and Building Security the exact location of the participant within the building

- Notify the Project Coordinator or another Full Time staff person on the team to stay with the participant and the primary staff person.
- Go to the building entrance to meet EMS and direct them to the participant.
- **Primary Staff Person:**
  - You are to stay with the participant until help arrives.
  - Please clear the immediate area so First Responders have room to respond and get to the participant when they arrive.
  - Please limit the number of people near the participant so there is room for the first responders when they arrive. No crowds.
- **Primary Staff Person (IF trained on naloxone administration):**
  - If you assess the participant according to your training and determine that they meet the criteria for naloxone, loudly announce to the participant, "**I am going to give you naloxone now.**"
  - You may administer the Naloxone Kit\*\* according to the instructions, starting with one dose of naloxone. The administration of the Naloxone Kit covers up to two doses.
- **Primary Staff Person:**
  - Notify the First Responders immediately if naloxone is administered, and how much was administered.
  - Disclose at least the first name of the participant to First Responders, as well as any relevant health information (if received), and that this may be an opioid overdose.
- **All Staff Involved:**
  - Once the First Responders arrive to the location and have located the participant, these professional medical staff become immediately responsible for all first aid procedures.
  - Back away and give the First Responders space. Make sure the area is clear so they can leave quickly if needed.

## **E1. Regulatory Issues**

### **Reporting of Unanticipated, Adverse, or Severe Adverse Events (SAEs)**

The overall data and safety monitoring will be the responsibility of the Principal Investigator (PI), [name] [name]. The PI is also responsible for executing the Data and Safety Monitoring Plan (DSMP), and complying with the reporting requirements. The PI will provide a summary of the DSMP report to the National Institute on Drug Abuse (NIDA) on an annual basis as part of the progress report.

The PI will ensure that all study procedures are in place prior to the initiation of the protocol, and that all study procedures and reporting of adverse events are performed according to the protocol. Severe adverse events (SAEs) will be monitored by the investigative team in near real-time throughout the trial. In addition, a Data Safety Monitoring Board (DSMB) will also provide independent study monitoring during all patient recruitment activities as described below.

The PI will monitor for adverse events that change study risk level. If an adverse event occurs which changes the study risk level, the Study PI will immediately report this event to the IRB (Brown University), DSMB, and NIDA, and will oversee the process of modifying the study as appropriate to

address the change in risk. The PI will also provide annual reports summarizing SAE data to the IRB.

Given the nature of our eligibility criteria, the most severe adverse event may include fatal overdose among participants in the clinical trial. Overdose fatalities in Rhode Island are at crisis levels. Therefore, we may reasonably expect an outcome of fatal overdose among some participants. Given the severity of such an event, the PI will also monitor for self-reported, nonfatal overdoses (at follow-up visits). Each self-reported or fatal overdose will qualify for review by the DSMB to ensure any overdoses among our participants are not related to their participation in the research and are not more prevalent than expected (see below: *Collection and Reporting of Adverse Events [AE] and Severe Adverse Events [SAEs]*). All fatal overdose events occurring in the state are certified by the Office of State Medical Examiners within 90 days. To ascertain fatal overdose events, we will obtain consent from participants at the start of the trial to link to overdose surveillance datasets with participant data using a probabilistic linkage with the following combination of identifiers: first and last name, date of birth, and sex.

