#### **Data Transfers** – there are select methods to import data, including but not limited to:

- Select Rhode Island state agencies and other offices using a secure VPN tunnel
- Encrypted USB drives
- Secure transfer through firewall exception
- Import and export servers

For the proposed project, the Senior Research Assistant will conduct and automate secure data transfer of administrative overdose records with RIDOH on a monthly basis (according to the timeline outlined in our existing data use agreement).

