## **Collection and Reporting of Adverse Events (AE) and Severe Adverse Events (SAEs)**

### **FDA Definitions**

SAEs must be reported to the NIDA PO within 24 hours of the event by email. At a minimum this 24 hour notification should include a brief explanation of the SAE and when it occurred. A written follow up must be received within 72 hours of the event. The written follow up should include information on the date of the event, what occurred, actions taken by project staff, planned follow up (if any), the intervention group/study arm of the affected participant, whether the event appears to be related to the intervention, and whether participant will continue in the study).

AEs must be reported to the NIDA PO at least once per year and can be reported as a part of the annual progress report. At a minimum, this report should describe the event, when it occurred, the study arm of the participant, and the outcome/resolution. If there were no AEs, a statement that no AEs occurred should be included in the progress report or communicated to the PO in writing.

Our research team will follow FDA federal guidelines for reporting of all Adverse Events and Severe Adverse Events. The level of study risk, Adverse Events, and Severe Adverse Events will all be monitored and managed throughout the study by the Project Investigator with support from the Project Director.

Consultation from the Brown IRB will be immediately available to the PI to address any required actions, investigations, or changes to the risk level of the study.

The DSMB will be notified within 24 hours of any severe adverse events, and will be asked to convene at the earliest possible time to discuss, but no greater than 30 days from the time of the severe adverse event notification. A detailed summary of AEs will be reported to the DSMB on a quarterly basis.

The following AEs will be reported to the DSMB:

- Participant concerns or complaints regarding the fentanyl test strip devices
- Findings from other studies regarding device risk
- Self-reported nonfatal overdose (determined through study assessments)
- Severe discomfort due to assessment procedures
- Significant embarrassment in disclosing sensitive personal information

The following SAEs will be reported to the NIDA PO and the DSMB:

- Violation of confidentiality or breach of participant records with PII
- Overdose death (determined through record linkage)

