- Death from other causes (determined through participant follow-up procedures)
- Overdose on-site at the research study
- Unanticipated adverse device effects
- Disclosure of information about current and/or intended physical harm to persons; current and/or intended abuse of children that would be reported to a child welfare agency; and/or an investigation of such allegation(s) that could ensue

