## **G1. Trial Efficacy**

### **Plans for Interim Analysis of Efficacy Data**

The primary data will be analyzed and reviewed on a monthly basis by the Biostatistician, and on quarterly intervals by the project Investigators. For the overdose surveillance data that are provided by RIDOH, the Data Analyst and Senior Research Assistant will analyze and clean those data on a monthly basis and present summarized results to the project investigators quarterly.

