#### Assessing intervention efficacy in reducing fatal and nonfatal overdose (Aim 1, primary endpoint).

The primary outcome will be **non-fatal overdose**, defined as a composite outcome, consisting of one of the following:

1. A self-reported overdose ascertained at the six and/or 12 month follow-up visits;
2. A non-fatal opioid overdose identified in the Rhode Island EMS database, using a case definition for suspected overdose developed by RIDOH previously;
3. An emergency department encounter for an accidental drug overdose that did not result in death, using a case definition developed by the CDC;

The primary analysis will be conducted using a survival framework, with time to *first* nonfatal overdose—identified through any of the data sources noted above—serving as the primary outcome. For self-reported data, event times will be estimated from SAE reports (in which participants are asked to estimate the date of their overdose). Participants will be right-censored as of the date of the first

---

 <https://www.ncbi.nlm.nih.gov/pmc/articles/PMC7948191/>

outcome event or at the end of the follow-up period, defined as 15 months following the participant's baseline visit.

To account for potential imbalance and to improve statistical efficiency, we will adjust for known or anticipated prognostic variables measured at baseline. These variables will include sociodemographic characteristics (e.g., age, gender identity, race/ethnicity), recent criminal justice involvement, housing instability, and substance use patterns including injection drug use & history of overdose. Variables will be transformed or categorized as necessary to address skewed or imbalanced data. We will also adjust for pre-baseline EMS runs for suspected opioid overdoses and ED encounters for drug overdoses using the case definitions noted above, occurring up to six months prior to the date of the participant's baseline visit.

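### The DSMP's list of overdoses reported to the DSMB does not name non-fatal overdoses found by EMS or ED linkage, although the SAP counts them in the primary endpoint

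*Protocol*

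**What the plan says.** **What the board receives.** DSMP section E1 (reporting of adverse events) says "Each self-reported or fatal overdose will qualify for review by the DSMB", so that the board can check that overdoses are unrelated to participation and no more frequent than expected. The lists in DSMP section F1 name three kinds of overdose:

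- as an adverse event, "Self-reported nonfatal overdose (determined through study assessments";
- as a severe adverse event, "Overdose death (determined through record linkage";
- as a severe adverse event, "Overdose on-site at the research study".

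Under Trial Stopping Rules in E1, the biostatistician summarises these events each quarter and flags any category with a significant excess in the intervention arm (p < 0.05, two-sided).

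**What the trial counts.** SAP section 3 defines the primary outcome as a composite of self-report, "A non-fatal opioid overdose identified in the Rhode Island EMS database", and "An emergency department encounter for an accidental drug overdose that did not result in death".

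**Where the linked data go.** DSMP section C1 provides for "secure data transfer of administrative overdose records with RIDOH on a monthly basis". DSMP section G1 has staff analyse the health department's surveillance data monthly and "present summarized results to the project investigators quarterly". The DSMB is not named there.

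**Interim analyses.** SAP section 4 uses self-reported non-fatal overdose as the information measure. It places a first look, for harm, at about one third of the sample followed to 12 months, and a second, for efficacy, at about two thirds. SAP section 5 says the second look follows the analysis already described, which points to the composite.

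**The concern.** An overdose that brings an ambulance or an ED visit is among the most serious that a participant survives. Under the DSMP as written, it reaches the board only if the participant attends a later visit and reports it. Record linkage feeds the board's list for deaths alone.

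The Protocol itself names false reassurance from a negative strip as a risk of the intervention (section 3.4). The non-significant-risk justification (Attachment H) leans on reporting of adverse events to the DSMB. If the routine reports leave out serious non-fatal events in people who stop attending, the board judges harm on data that depend on attendance and recall. If attendance also differed by arm, the comparison would be biased. The excess-incidence flag works on event categories, so it cannot respond to a category that does not exist.

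**Working it through.** **1. Endpoint components against the DSMB list**

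| Event | In SAP primary endpoint | Named in DSMP E1/F1 for the DSMB |
|---|---|---|
| Self-reported non-fatal overdose | yes | yes |
| EMS-linked non-fatal overdose | yes | no |
| ED-linked non-fatal overdose | yes | no |
| Overdose death by linkage | no (exploratory endpoint) | yes |
| On-site overdose | not separately | yes |

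The general statement in Trial Stopping Rules that all adverse events go to the board refers the reader forward to the F1 list, so it does not widen it. SAP section 3 describes the reported events as coming from participants, and SAP section 5 gives self-report as its only example.

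**2. The plan's own figures.** SAP section 6 assumes 250 per arm, 20% of controls with an overdose in 12 months, 80% retention, and 38% of overdoses ending in death or EMS attendance (the DSMP version says death or ED presentation).

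- 0.38 × 20% = 7.6%, which agrees with the stated 8 per 100 person-years after rounding.
- 250 × 0.80 = 200 per arm; 20% v 10%, two-sided 0.05, gives power 0.802, which agrees with the stated >80%. The point does not depend on this figure.

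**3. Size of the gap, no treatment effect**

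- Participants with an overdose: 500 × 0.20 = 100
- With a severe one: 100 × 0.38 = 38
- Of these, not retained: 38 × 0.20 = 7.6, or 3.8 per arm

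With the planned 50% reduction: 3.8 control + 250 × 0.10 × 0.38 × 0.20 = 1.9 intervention, total 5.7.

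The 7.6 treats every severe event in a non-retained person as unseen and as non-fatal. Each follow-up survey asks about overdose since the last visit, so only events after the last attended visit are hidden. If half came earlier (an assumption; the plan gives no timing of loss), the figure is 7.6 × 0.5 = 3.8 across both arms. The 38% includes deaths, which the board does receive.

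**4. Range for the control arm (assumed inputs)**

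- Low: loss 10%, share 20%: 250 × 0.20 × 0.10 × 0.20 = 1.0
- High: loss 30%, share 60%: 250 × 0.20 × 0.30 × 0.60 = 9.0
- If attenders also fail to report 10% to 30% of linked events, at 20% loss and a 38% share: 19 × (0.20 + 0.80 × 0.10) = 5.3 to 19 × (0.20 + 0.80 × 0.30) = 8.4

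**5. Delay for attenders**

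- Protocol Table 1, visits at months 1, 2, 3, 6, 12: longest gaps 6 − 3 = 3 and 12 − 6 = 6 months.
- DSMP section A1, months 1, 2, 3 plus 4, 8, 12: longest gap 4 months.

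The two schedules contradict each other and must be reconciled.

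**The case against.** The strongest reply is that the documents are silent rather than exclusive. The SAP is an appendix to a DSMB charter whose body is not among the documents, and the charter may set the contents of board reports. Both documents say that all adverse events are reported to the board and let it act on other safety data. SAP section 5 calls the study outcome a severe adverse event and offers self-report only as an example. DSMP section E1 sends any event that changes the study's risk level to the board at once. The mismatch also looks like version lag: the SAP cites a 2022 EMS case definition, while the last approval stamped on the Protocol is December 2021, and the DSMP limits linked outcomes to deaths.

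Much of this stands, and it rules out some stronger readings that a reader might infer:

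- *That a harm signal would never reach the board.* The second interim analysis appears to use the composite.
- *That investigators see by-arm data withheld from the board.* DSMP section G1 does not say that its summaries are by arm, or that they contain non-fatal events matched to participants.
- *That linked ED data arrive monthly.* The monthly transfer is stated for administrative overdose records in general. The SAP gives no frequency, and none is stated for hospital discharge data. Protocol section 3.1e also leaves the consent for linkage to a future amendment.
- *That 7 to 8 is an estimate.* It is an upper figure on the plan's inputs.
- *That the comparison between arms is biased.* This needs attendance to differ by arm, and no figure in the documents shows that it does.

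What does not stand is the suggestion that the general wording closes the gap. It leads back to the list that omits these events, and the second interim comes too late to replace periodic safety reporting.

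**Conclusion.** The concern holds as an omission between documents. The DSMP's reporting list was not extended when the SAP made EMS- and ED-linked non-fatal overdoses two of three primary-endpoint components, and no section brings them into the board's periodic safety reports or the excess-incidence flag.

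The size is modest: at most about 7 to 8 participants across both arms on the plan's figures, assuming no treatment effect and loss unrelated to overdose, and fewer if some events precede the last attended visit or are fatal. For attenders it is a delay of up to 6 months, or 4 on the DSMP schedule. The documents do not show that the board is deliberately excluded. Still, staff who followed the list as written would leave these events out, so this is more than a missing detail.

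**What to change.** - In DSMP sections E1 and F1, add non-fatal overdose found through EMS or ED record linkage to the events reported to the DSMB. It then becomes a category under the excess-incidence flag.
- In each periodic DSMB report, and in the summaries under SAP section 5, tabulate by arm the self-reported, EMS-linked, ED-linked and fatal overdoses, de-duplicated by person and date. Give the date through which each source is complete.
- In DSMP section G1, state that any summaries given to the investigators are pooled and not by arm.
- Reconcile the two visit schedules. Also reconcile the classification of self-reported overdose, which is an adverse event in DSMP F1 and a severe adverse event in SAP sections 3 and 5.

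The cost is wording plus one table from sources that the primary analysis needs anyway. The table can be only as current as the transfers and the linkage consent allow, hence the completeness dates. The downside is the de-duplication work and some re-classification as source records are finalised.

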### **Report of Changes or Amendments to the Protocol**

All changes or amendments to the protocol will be submitted in writing and will receive prior approval from the Brown University IRB. We will also seek approval from the NIDA program officer (PO) as well. Significant protocol changes will be uploaded to clinicaltrials.gov upon IRB and NIDA approval.

### **Trial Stopping Rules**

Interim analyses of study data are planned according to the alpha spending rule [Lan and DeMets, 1994]. The proportion of expected events (i.e., self-reported non-fatal overdose) is considered as the information statistic. The *p*-values will be constructed to maintain the overall study power of 0.05, two-sided. If the test statistic exceeds the boundary, then the study could be considered for early termination due to emerging differences between the two arms. The PI will recommend to the DSMB that two interim analyses should be conducted over the course of the study.

The study investigators will report all adverse events and significant adverse events to the DSMB (see below). Moreover, all adverse and significant adverse events will be summarized by the study Biostatistician each quarter, and all categories with a statistically significant (at a *p* < 0.05, two-sided) excess incidence in the intervention group will be flagged. These flags will be reviewed and commented on by the DSMB, which may recommend early termination of the trial given evidence of harm based on these and other safety data.

Finally, the entire trial will stop if any investigator judges it necessary for medical, safety, regulatory, or other reasons consistent with applicable laws, regulations, or good clinical practice. Once a concern of this proportion is raised, the decision to stop the trial will be made through immediate consultation with the IRB, the DSMB, and NIDA.

### **Disclosure of any Conflict of Interest**

All data sharing partners (e.g., RIDOH) and project investigators will agree to specific terms of use for the data according to a signed Data Use Agreement, which includes a request to disclose any potential conflicts of interest.

All individuals who meet the definition of Investigator will participate in Brown's FCOI or equivalent

Brown University IRB Original Approval: 4/18/2019

Brown University IRB Amendment Approval: 11/22/2019

<https://IRB.AmendmentApproval/01b/202d/7973215>

Brown University IRB Amendment Approval: 10/15/2020

Brown University IRB Amendment Approval: 02/26/2021

Brown University IRB Continuing Review Approval: 03/18/2021

Brown University IRB Amendment Approval: 06/15/2021

Brown University IRB Amendment Approval: 09/01/2021

Brown University IRB Amendment Approval: 10/05/2021

Brown University IRB Amendment Approval: 11/09/2021

Brown University IRB Amendment Approval: 12/13/2021

training, and sign all necessary forms related to disclosure of conflicts of interest.

## **Data Safety**

This project will use Brown University's Stronghold secure computing environment. As described in section F1, this computing environment is HIPAA aligned, and developed for housing, sharing, and analyzing sensitive data.

### **F1. Trial Safety**

#### **Potential Risks and Benefits for Participants: Loss of Confidentiality**

This project uses primary and secondary data regarding illicit drug use and overdose events; therefore, confidentiality of study data is of utmost importance. Access to such records for legitimate research purposes has been approved by our data sharing partner, RIDOH, and our team has worked carefully to ensure the protection of these data.

We recognize that a loss of confidentiality may also result in psychological harm to individuals or in social harm. As such, the research team will be using Brown's state of the art Stronghold computing environment for the transfer, analysis, and protection of all research data. Data sharing partners will share only the required datasets and variables. Additionally, only select members of the analytic team will have access to any identifiable datasets. All data transfer procedures, analytic plans, and use of administrative datasets will be approved by the Brown IRB.

#### **Potential Risks and Benefits for Participants: Referrals for services or treatment**

To determine if participants would benefit from referrals for treatment or social services, we will offer all participants a community resources packet at the end of the baseline visit. These resources will include information regarding addiction treatment (including MAT), syringe exchange, peer counseling, and mental health care. We will then ask if they would be willing to hear about programs or organizations pertaining to those services most important to them. Based on their responses, we can then refer them to those specific organizations.

